## 2 Study Objectives

Primary objective for pilot study:

1. To evaluate the feasibility of patient randomization, accrual, and tissue collection in a pilot study of metformin versus observation following resection of stage IA-IIIA lung squamous cell cancer for patients.
2. To compare the 2-year recurrence free survival (RFS) rate between metformin and observation.

[figure not shown]
Secondary objective(s) for pilot study:

1. To develop the metformin sensitivity index based on iPS cell lines from the first 20 patients randomized to the metformin arm.
2. To apply the metformin sensitivity index on the remaining 25 patients randomized to metformin and the 45 observation patients (70patients total) to compare the 2-year RFS rate between metformin-sensitive and metformin-not-sensitive patients
3. To compare adverse events between metformin and observation arms using CTCAE version 4.

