## 3 Study Design

### 3.1 General Design

Patients will be identified and enrolled from Thoracic Surgical Clinics. Patients will undergo surgical resection with the collection of tumor tissue, normal lung tissue, blood, and skin biopsies. For patients enrolled in the study that were found to have stage IA-IIIA SCC, starting less than 90 days from the time of surgery, patients will be randomized to receive either 850 mg po BID of metformin or observation. Metformin dosing will include a 4 week ramp up of 850 mg po daily prior to starting the BID dose, for a total of 6 months of Metformin. Patients will be followed for 2 years from the time of surgery to evaluate 2-year RFS. We plan to randomize a total of 100 patients (50 per arm), such that 90 patients are evaluable for the primary endpoint.

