## 7 Statistical Plan

### 7.1 Statistical Methods

All patients meeting the eligibility criteria, and who started treatment, will be considered evaluable for the 2 year RFS rate endpoint. The proportion of 2 year RFS rates (along with the 95% confidence interval) will be estimated within each arm by the number of patients who are recurrence-free and alive at 2 years divided by the total number of evaluable patients in each arm, and compared using a chi-squared test.

Clinical data regarding recurrence-free survival (RFS) will be utilized for development of the metformin sensitivity index. Data collected will be summarized using descriptive statistics, including mean and standard deviation and median and inter quartile range for continuous variables, and using frequencies and percentages for categorical variables. Logistic regression models will be used to assess the impact of metformin sensitivity index metrics, treatment, and the interaction between the metformin sensitivity index metrics and treatment on the 2 year RFS status as the outcome of interest.

Adverse events (AEs) will be compared between metformin and placebo using CTCAE version 4. To evaluate the AE profiles associated with each intervention arm, the maximum grade for each type of AE will be recorded for each participant and frequency tables will be reviewed to determine the overall patterns. The number and severity of AEs (overall and by intervention group) will be tabulated and summarized across all grades. Chi-square tests will be used to compare the AE rates between metformin and placebo.

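### The index-by-treatment interaction model names no test and no method for separation; with a two-class index in 25 metformin and 45 observation patients, a strong effect can leave the odds ratio infinite and Wald inference unusable

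*Combined protocol and SAP*

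**What the plan says.** Section 7.1 (Statistical Methods) gives the model in one sentence: "Logistic regression models will be used to assess the impact of metformin sensitivity index metrics, treatment, and the interaction" of the two. The outcome is binary, since the model concerns "the interaction between the metformin sensitivity index metrics and treatment on the 2 year RFS status as the outcome of interest". The section does not name the interaction test (Wald, likelihood-ratio or other), a method for sparse cells or separation, the form in which the index metrics enter, or the patients included.

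Section 2 (Study Objectives) supplies some of the context. The index is built on "iPS cell lines from the first 20 patients randomized to the metformin arm". Secondary objective 2 is then "To apply the metformin sensitivity index on the remaining 25 patients randomized to metformin and the 45 observation patients", 70 patients in total, in order "to compare the 2-year RFS rate between metformin-sensitive and metformin-not-sensitive patients". That wording implies two index classes. Section 3.1 gives the overall size: "We plan to randomize a total of 100 patients (50 per arm), such that 90 patients are evaluable for the primary endpoint".

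Neither section gives a prevalence of metformin sensitivity, a 2-year failure rate, an interaction size, or an alpha or power for this analysis.

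**The concern.** The interaction is the term that separates sensitivity to metformin from plain prognosis. A main effect of the index could mean only that sensitive patients do better on either arm. What carries most of the information on the interaction is the outcome in metformin-treated, index-sensitive patients, and that cell is small: 25 patients are split in two.

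If metformin works well in those patients, few of them fail, and the cell may contain no failure at all. Ordinary maximum likelihood then has no finite interaction estimate, and the Wald p-value that much software prints by default goes towards 1. If the analyst relied on that output, a strong effect could be reported as not estimable and not significant. If the analyst instead chose a test after seeing the problem, the choice would be data-driven. The plan closes off neither route. The pilot is meant to supply preliminary data for a larger trial and a metformin response index (Introduction), so the handling of this one term matters even for a secondary objective.

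**Working it through.** **Patient numbers.** Section 2 gives 20 metformin patients for building the index, then 25 metformin and 45 observation patients: 25 + 45 = 70 and 20 + 25 + 45 = 90. The 90 agrees with the evaluable number in section 3.1. There is no stated power for the interaction to reproduce.

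**Assumed inputs (not in the documents).** Prevalence of sensitivity 30%, 40% or 50%. Two-year failure 40% in the other three cells. Failure in the metformin-sensitive cell 10% (strong effect) or 20% (halved). Two-sided 0.05. The only related figure in the documents is a recurrence range of 30-70% by stage (section 1.1). It is not a 2-year rate and does not include death.

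**Cell size.** 25 × 0.30 = 7.5; 25 × 0.40 = 10; 25 × 0.50 = 12.5. So about 8 to 13 patients.

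**Chance of no failure in that cell.** Each metformin patient is a sensitive patient who fails with probability prevalence × failure rate, so

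P(no failure) = (1 − prevalence × failure rate)^25.

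| Prevalence | 10% failure | 20% failure | 40% failure (no effect) |
|---|---|---|---|
| 30% | 0.97^25 = 47% | 0.94^25 = 21% | 0.88^25 = 4% |
| 40% | 0.96^25 = 36% | 0.92^25 = 12% | 0.84^25 = 1% |
| 50% | 0.95^25 = 28% | 0.90^25 = 7% | 0.80^25 = 0.4% |

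Simulation gave 45%, 37% and 30% for the first column and 21%, 12% and 7% for the second, in agreement within simulation error.

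**What then happens to the estimate.** With two classes and two arms the model is saturated, and the interaction log odds ratio is a sum and difference of four cell logits. Take an illustrative table at 40% prevalence:

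- metformin-sensitive: 0 failures of 10
- metformin, not sensitive: 6 of 15
- observation, sensitive: 7 of 18
- observation, not sensitive: 11 of 27

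Maximum likelihood gives [(0/10)/(6/9)] / [(7/11)/(11/16)] = 0. The log is minus infinity, its standard error diverges, and the Wald statistic goes to 0.

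In a saturated model, Firth's method amounts to adding one half to the failures and one half to the non-failures in each cell: [(0.5/10.5)/(6.5/9.5)] / [(7.5/11.5)/(11.5/16.5)] = 0.0696/0.9357 = 0.074. This is finite.

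**Power for the interaction, simulated, 10% against 40% failure.** Separated fits count as Wald non-rejections.

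| Prevalence | Wald | Firth penalised LR | Ordinary LR |
|---|---|---|---|
| 30% | 3% | 16% | 28% |
| 40% | 8% | 23% | 36% |
| 50% | 11% | 28% | 37% |

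Type I error is about 4-6% for Firth and 6-7% for the ordinary likelihood-ratio (LR) test. Among trials with no failure in the metformin-sensitive cell, the ordinary likelihood-ratio test still rejects in 53-76%.

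**Sensitivity to the two readings.** With a continuous index, separation occurred in 0.6% or less of trials in every scenario tried. If all 90 evaluable patients entered (45 on metformin), the chance of no failure at a 10% rate would be 0.97^45 = 25% at 30% prevalence and 0.95^45 = 10% at 50%.

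**The case against.** A good deal stands on the other side.

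- **The plan does not specify a Wald test.** A reader might infer that the analysis as planned would return a p-value near 1 whenever the drug works. Section 7.1 says only that logistic regression will be used, which leaves likelihood-ratio and profile-likelihood inference open. The ordinary likelihood-ratio test keeps 28-37% power in the same scenario, so it would be wrong to say that the model breaks down or that a true signal must be missed. What fails is the point estimate and Wald inference.
- **Firth is not a route to more power.** Its advantage over Wald comes from leaving Wald. Its raw power is below that of the ordinary likelihood-ratio test, although part of that gap reflects the latter's liberal type I error.
- **The size depends on a strong effect.** The 10% against 40% scenario is a four-fold reduction. With failure halved from 50% to 25%, the formula gives 14%, 7% and 4%. Nor does separation always rise with the effect. At a 70% baseline, halving the rate gives slightly less separation in any cell (8% and 3% at 30% and 50% prevalence) than no effect (11% and 4%).
- **Two premises are inferred.** Section 7.1 speaks of index metrics without saying that they are dichotomised, and it does not tie the model to the 70 patients. Both come from secondary objective 2.
- **It is a secondary objective of a pilot**, and no method makes 70 patients adequate for an interaction test.

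These points limit the size of the concern. They do not remove the gap: on one data set the answer can turn on the choice of test, and the plan leaves that choice open.

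**Conclusion.** The concern holds in a conditional form. Section 7.1 plans plain logistic regression for the interaction and specifies neither the test nor what to do under separation. If the index enters as two classes and the model is fitted in the 25 + 45 patients, the metformin-sensitive cell has no failures in about 30-45% of trials under a strong effect (10% against 40% failure), and in about 7-21% if failure is halved to 20%, over 30-50% prevalence. In those trials the interaction odds ratio is infinite and Wald inference is unusable, and Wald power over all trials in the strong-effect case is about 3-11%. An ordinary likelihood-ratio test remains workable but slightly liberal, and its point estimate is still infinite. With a continuous index the problem nearly disappears.

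All prevalences and failure rates are assumptions. The documents do not support the stronger conclusions that the cell will often have no failures whatever the effect, or that the planned analysis is bound to hide a true signal. This is a worthwhile correction to a secondary analysis and does not touch the primary objectives.

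**What to change.** In section 7.1:

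1. State that the index, treatment and interaction model is fitted in the 70 patients not used to build the index.
2. Enter one index score, locked before it is applied to those patients, and say whether it is binary or continuous. Do not enter several metrics at once, since each adds a main effect and an interaction.
3. Fit the model by Firth's penalised likelihood. Report the penalised likelihood-ratio test and the profile-likelihood 95% confidence interval for the interaction in place of Wald results.
4. Describe the result as an estimate with its interval, not as a confirmatory test.

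The cost is wording only; the method is available in standard software and needs no further patients or data. The downside is slight shrinkage of the odds ratios and somewhat lower raw power than the liberal ordinary likelihood-ratio test. In return, the estimate is finite, the type I error is about 4-6%, and the test is chosen before the data are seen.

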## 8 Safety and Adverse Events

### 8.1 Definitions

#### Unanticipated Problems Involving Risk to Subjects or Others (UPIRTSO)

Any unanticipated problem or adverse event that meets the following three criteria:

- Serious: Serious problems or events that results in significant harm, (which may be physical, psychological, financial, social, economic, or legal) or increased risk for the subject or others (including individuals who are not research subjects). These include: (1) death; (2) life threatening adverse experience; (3) hospitalization - inpatient, new, or prolonged; (4) disability/incapacity - persistent or significant; (5) birth defect/anomaly; (6) breach of confidentiality and (7) other problems, events, or new information (i.e. publications, DSMB reports, interim findings, product labeling change) that in the opinion of the local investigator may adversely affect the rights, safety, or welfare of the subjects or others, or substantially compromise the research data, **AND**
- Unanticipated: (i.e. unexpected) problems or events are those that are not already described as potential risks in the protocol, consent document, not listed in the Investigator's Brochure, or not part of an underlying disease. A problem or event is "unanticipated" when it was unforeseeable at the time of its occurrence. A problem or event is "unanticipated" when it occurs at an increased frequency or at an increased severity than expected, **AND**
- Related: A problem or event is "related" if it is possibly related to the research procedures.

### **Adverse Event**

An untoward or undesirable experience associated with the use of a medical product (i.e. drug, device, biologic) in a patient or research subject.

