### **Adverse Event Reporting Period**

Adverse events will be reported after the subject begins taking the metformin or starts the observation period. The bronchoscopy and surgery are considered standard of care.

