### **Preexisting Condition**

A preexisting condition is one that is present at the start of the study. A preexisting condition should be recorded as an adverse event if the frequency, intensity, or the character of the condition worsens during the study period.

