## **8.2 Recording of Adverse Events**

At each contact with the subject, the study team must seek information on adverse events by specific questioning and, as appropriate, by examination. Information on all adverse events should be recorded immediately in the source document, and also on the appropriate adverse event worksheet. All clearly related signs, symptoms, and abnormal diagnostic, laboratory or procedure results should be recorded in the source document.

All adverse events occurring during the study period must be recorded. The clinical course of each event should be followed until resolution, stabilization, or until it has been ultimately determined that the study treatment or participation is not the probable cause. Serious adverse events that are still ongoing at the end of the study period must be followed up, to determine the final outcome. Any serious adverse event that occurs after the study period and is considered to be at least possibly related to the study treatment or study participation should be recorded and reported immediately.

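### The adverse event definition in 8.1 is tied to use of a medical product, which fits a metformin-versus-observation comparison poorly and should be aligned with the plan's own both-arm recording rules

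*Combined protocol and SAP*

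**What the plan says.** All references are to the combined protocol and SAP.

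- **Definition.** Section 8.1, Adverse Event: "An untoward or undesirable experience associated with the use of a medical product (i.e. drug, device, biologic) in a patient or research subject". The Serious Adverse Event definition that follows sorts adverse events into serious and non-serious, so it takes over the same starting condition.
- **Comparison.** Section 2, secondary objective 3: "To compare adverse events between metformin and observation arms using CTCAE version 4". Section 7.1: "Chi-square tests will be used to compare the AE rates between metformin and placebo". No arm receives placebo. Sections 2 and 3.1 name observation as the control.
- **Start of reporting.** Section 8.1, Adverse Event Reporting Period: "Adverse events will be reported after the subject begins taking the metformin or starts the observation period".
- **Recording.** Section 8.2: "All adverse events occurring during the study period must be recorded". Also: "At each contact with the subject, the study team must seek information on adverse events by specific questioning". One stopping point for following an event is "until it has been ultimately determined that the study treatment or participation is not the probable cause".
- **Preexisting conditions.** Section 8.1: "A preexisting condition should be recorded as an adverse event if the frequency, intensity, or the character of the condition worsens during the study period". This rule mentions no product.

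**The concern.** A chi-square comparison of event rates is interpretable only if the same occurrence is counted by the same rule in both arms. The stated rule asks whether an occurrence is associated with use of a medical product. Every treated metformin patient is using such a product by design. An observation patient is given none by the study and would meet the condition only through some other medication or device.

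The setting leaves room for this to matter. There is no blinding: under section 5.3 the study team opens the allocation envelope, and under section 8.2 the study team records the events. The main toxicity expected of metformin is gastrointestinal (sections 1.1 and 1.2), and such symptoms are non-specific. Staff who apply the definition literally could log diarrhea in a metformin patient and leave out the same symptom in an observation patient. An apparent excess on metformin could then arise partly from the rule for counting, and it would carry into serious events.

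**Working it through.** **Step 1: does another passage replace the definition?** Set side by side, the passages of section 8 pull in two directions.

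| Place | What it does | Product link needed? |
|---|---|---|
| 8.1 Adverse Event | Defines the term | Yes, a medical product of any kind |
| 8.1 Serious Adverse Event | Classifies adverse events | Inherited from the definition |
| 8.1 General Physical Examination Findings | New findings at study end count if they satisfy the definition | Inherited |
| 8.1 Hospitalization, Prolonged Hospitalization or Surgery | A condition leading to surgery counts if it satisfies the criteria | Inherited |
| 8.1 Adverse Event Reporting Period | Starts reporting in both arms | Silent; uses the defined term |
| 8.1 Preexisting Condition | Worsening counts | No |
| 8.2 Recording of Adverse Events | Record all events, ask at each contact, follow until cause is settled | Silent on entry; implies that unrelated events are already on record |

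The reporting-period and recording rules show that collection is meant to cover both arms. They use the defined term without redefining it, and two passages send staff back to the definition. The preexisting-condition rule drops the product link, but only for worsening of something already present. For a new symptom in an observation patient, the written definition and the evident intent disagree.

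**Step 2: what would happen if some observation-arm events went uncounted?** The plan gives no expected adverse event rate, significance level or detectable difference for this comparison, so there is no figure of its own to reproduce. The inputs are:

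- *n* = 45 per arm. This is half of the 90 patients in section 3.1 who are to be evaluable for the primary endpoint. The plan states no analysis set for adverse events; 50 per arm are randomized.
- True rate of an event type *p* = 0.30 in both arms (assumed).
- Two-sided 5% test (assumed).
- Share *m* of observation-arm events not counted (assumed; the documents give none).

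The recorded observation rate is *q* = *p*(1 − *m*). With p̄ = (*p* + *q*)/2, the standard errors are

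s0 = √[2p̄(1 − p̄)/n] and s1 = √{[p(1 − p) + q(1 − q)]/n},

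and the chance of declaring an excess on metformin is about Φ[(p − q − 1.96·s0)/s1].

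For *m* = 0.5: q = 0.15 and p̄ = 0.225. Then s0 = √(2 × 0.225 × 0.775/45) = 0.0880 and s1 = √[(0.2100 + 0.1275)/45] = 0.0866. The argument is (0.15 − 0.1725)/0.0866 = −0.26, which gives about 40%.

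Exact enumeration of the two binomial distributions, with the uncorrected chi-square test, gives the probability of rejection in either direction:

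| Share uncounted | Recorded rates, metformin v observation | False-positive rate |
|---|---|---|
| 0 | 30% v 30% | about 5% |
| 25% | 30% v 22.5% | 13% |
| 50% | 30% v 15% | 42% (normal approximation 40%) |

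**Step 3: sensitivity to the assumed rate and sample size.** Exact results for other true rates:

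| Per arm | Share uncounted | True rate 20% | 40% | 60% |
|---|---|---|---|---|
| 45 | 25% | 10.1% | 17.4% | 28.3% |
| 45 | 50% | 27.7% | 56.3% | 81.8% |
| 50 | 25% | 10.6% | 18.0% | 34.5% |
| 50 | 50% | 30.3% | 59.5% | 87.6% |

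With nothing uncounted, the rate stays near 5% in every case.

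**The case against.** The strongest reply is that the literal reading adds words. The definition speaks of a medical product, not the study product, and of association, not causation. Observation patients are not shown to be free of medication; section 5.6 reviews medications in both arms before the study period starts. Read as a whole, section 8 starts reporting with the observation period, asks about events at every contact, counts worsening of preexisting conditions, and follows events until treatment or participation is ruled out as the cause. That last rule makes sense only if events later judged unrelated were already recorded. A reading that nearly empties the reporting-period rule and secondary objective 3 for one arm is not the natural one.

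Much of this stands. A reader might infer that the comparison is biased by the definition, or that observation-arm events will not be collected. The documents support neither. They point to an intended exclusion share of zero, and no passage supports a share of one quarter, one half or any other value. The illustration shows sensitivity only.

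Two things survive the reply. First, taking medical product broadly does not make the rule the same in both arms: metformin patients meet the product condition by design, observation patients only through incidental use. Second, the good intent sits in passages that rely on the defined term, so the disagreement is left to unblinded staff to settle case by case.

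It is also fair to say that the more firmly documented threat to this comparison lies elsewhere. Section 6.4 gives monthly calls about adverse events to the metformin group only, while section 6.5 follows all subjects every 6 months. That is a separate ascertainment problem.

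**Conclusion.** The definition is ill-suited to this comparison and inconsistent with the recording rules around it. If applied literally, it could lower the observation-arm count and bias the adverse event and serious adverse event comparison against metformin. Bias is possible, not demonstrated, and its size cannot be derived from the documents.

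The illustrative figures (about 5%, 13% and about 40% for none, a quarter and half uncounted) rest on 45 per arm, a 30% true rate in both arms and a two-sided 5% test. Only the 45 has a source in the plan, and it is borrowed from the primary endpoint.

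The point concerns the third secondary objective of a pilot. It is worth correcting because the correction is cheap and removes a judgment that depends on the arm.

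**What to change.** In section 8.1, define an adverse event as any untoward medical occurrence in a randomized subject from the start of metformin or of the observation period, in either arm, whether or not it is considered related. Record relatedness as a separate field on the adverse event worksheet. The serious adverse event definition and the passages that refer back to the term then follow without further change, and the definition agrees with the reporting-period and recording rules.

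The cost is one reworded definition, one data field and more observation-arm events to log.

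As a separate labeling correction, replace placebo with observation in the adverse event paragraph of section 7.1. This carries no weight in the argument above.

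The new definition does not deal with the metformin-only monthly calls in section 6.4. Equal contact would not give the arms a common definition, and a common definition would not equalize contact, so each needs its own change.
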